# 4.3. Randomization and study procedures

If patients fulfill all inclusion criteria, with no exclusion criteria and provide informed consent, they will be randomized in a 1:1 fashion into the intervention group or the control group according to a pre-specified, computer-generated, web-based randomization scheme using the secuTrial© Software (managed and secured by the Clinical trial Unit of the University of Basel). The randomization will be stratified for the site and initial NRS (Appendix 2). In both study groups, all patients will be re-assessed daily by the nutritional specialist to re-evaluate nutritional intake and whether nutritional targets are met. If patients in the intervention group do not reach the nutritional targets (<75%), their nutritional strategy will be escalated according to the nutritional guidelines.

We will systematically collect blood samples at admission (day 0) and on inpatient days 2, 4, 6 and 8 for later batch measurement of nutritional markers and other biomarkers. If clinically indicated, there will be pre-prandial measurement of blood glucose levels 4 times daily and insulin treatment in all patients as part of usual clinical practice. There will also be regular measurement of nutritional factors in blood and possibly 24 hour urine to assess the effectiveness of nutritional therapy (see CRF for further details).

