# 4.4. Initial patient assessment

After trial inclusion, each patient will receive a structured systematic medical and nutritional assessment by an experienced study-team member dietician according to the case report form (CRF) including:

- Socio-demographics (e.g., age, weight and height for calculation of body-mass index [BMI])

- If feasible, basal metabolic rate (BMR) calculated using indirect calorimetry; or if calorimetry is not feasible or tolerable, the Harris-Benedict formula will be used for estimation instead
- Baseline lean body mass (estimated with body impedance analysis [BIA])
- Baseline muscle strength (hand grip strength)
- Baseline functional status (Barthel's index)
- Medical diagnoses according to the ICD10-codes and nutritional diagnoses according to the IDNT reference manual (fourth edition)

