# 8.2. Statistical approach

Detailed methodology for summaries and statistical analyses of the data collected in this study will be documented in a statistical analysis plan. The statistical analysis plan will be finalized before database closure.

Briefly, a consort diagram will be reported including all screened patients, patients lost to follow up and patients included in the final analyses. Primary and secondary endpoints will be compared between trial arms in the overall ITT population and within predefined subgroups as discussed below. All outcomes will be analyzed in an uncorrected manner as well as jointly corrected for the main risk factors (Barthel's index at baseline, study center and initial NRS categories). For our primary analysis, we will compare the two arms with a chi-square test and we will also estimate effect size with a logistic regression model reporting unadjusted and adjusted odds ratios (OR) and corresponding 95% confidence intervals (CIs).

We will do different predefined subgroup analyses by including interaction terms in the regression models to test for effect modification by important baseline factors. Specifically, we will look at patients age (<60, 60-75, >75 years), gender, risk for undernutrition stratified according to initial NRS (3, 4, >4 points), BMI (<20, 20-25, >25-30, >30), main medical diagnosis (systemic infection, heart failure, acute renal failure, gastro-intestinal disease, tumor), comorbidities (diabetes, chronic renal failure).

For the analysis of functional outcome (defined by Barthel's index) we will use a non-parametric Wilcoxon rank sum test to compare Barthel's index at day 30 between randomization arms. However, to adjust for additional variables, we will also fit a multivariate linear model including Barthel's index at baseline, study center and initial NRS to estimate effect size and 95% confidence intervals (95%Cls). If needed, data will be transformed as appropriate (e.g., log transformation). Moreover, we will assess the progression of Barthel's index over time (i.e. admission, day 8, day 30) using a linear mixed model approach to account for the repeated measurements per patient.

A similar approach will be used for all other secondary endpoints where we will use chi-square tests / logistic regression analysis for binary outcomes, Wilcoxon rank sum test / linear models for continuous outcomes and log-rank test / cox regression for time-to-event data as appropriate.

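### Making the already planned adjusted logistic model the primary test would add power above plan; the unadjusted chi-square is valid but does not use site, NRS or baseline Barthel

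*Protocol*

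**What the plan says.** Protocol section 8.2 fixes the primary test: "For our primary analysis, we will compare the two arms with a chi-square test". It gives the regression a different job: "we will also estimate effect size with a logistic regression model reporting unadjusted and adjusted odds ratios (OR", with 95% confidence intervals. Just before that, it sets out a general policy: "All outcomes will be analyzed in an uncorrected manner as well as jointly corrected for the main risk factors". The risk factors it lists are baseline Barthel index, study centre and initial NRS category.

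Two of these three also govern allocation. Section 4.3 states: "The randomization will be stratified for the site and initial NRS". Section 4.4 includes the Barthel index in the initial assessment, so the third is collected as well.

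Section 8.3 sizes the trial for the same unadjusted Pearson chi-square: 40% against 34%, two-sided 5%, 1359 per group for 90% power, and a planned total of 2000 to 3000.

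**The concern.** The primary p-value comes from the less efficient of two analyses that the protocol already commits to. Section 8.2 itself regards baseline Barthel, centre and NRS as the main risk factors. If they predict the composite endpoint, a test that conditions on them has more power than one that does not. Baseline Barthel is also tied to the endpoint by construction, because component (e) in section 4.2 is a fall in Barthel from its admission value.

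The gain matters most at the low end of the recruitment range. Section 8.3 accepts 2000 patients at a stated 78% power, and section 15 concedes that 3000 in two years is ambitious.

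**Working it through.** **Step 1: reproduce the plan's figure.** Inputs from section 8.3: risks 0.40 and 0.34, two-sided alpha 0.05, power 0.90, 1:1 allocation. The mean risk is 0.37.

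n per group = [1.960·√(2·0.37·0.63) + 1.282·√(0.40·0.60 + 0.34·0.66)]² / 0.06² = [1.3382 + 0.8733]² / 0.0036 = 4.891 / 0.0036 = 1358.6, rounded up to 1359.

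This matches, and so do all nine rows of the sample size table. Power is 79.4% at 1000 per group, 90.0% at 1359 and 92.6% at 1500. The chi-square therefore delivers what section 8.3 states (78% at 2000; the 90% belongs to 2718).

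**Step 2: what adjustment would add.** The protocol gives no prognostic strength for site, NRS or Barthel, so ranges are assumed. Common set-up: 8 sites (section 3.3 names eight Swiss locations), 3 NRS strata (section 8.2 uses 3, 4 and >4), permuted blocks of 4 within the 24 strata (assumed), and marginal risks held at 40% and 34%. Strengths are on the logit scale: site SD / per NRS step / per SD of Barthel.

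Set B, 3000 simulated trials per cell, power in %:

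| Strength | Patients | Chi-square | Cochran-Mantel-Haenszel, site × NRS | Logistic: site, NRS, Barthel |
|---|---|---|---|---|
| None 0/0/0 | 2000 | 81.4 | 81.3 | 81.4 |
| | 2718 | 89.6 | 89.7 | 89.7 |
| Weak 0.2/0.15/0.3 | 2000 | 79.4 | 79.7 | 80.5 |
| | 2718 | 90.5 | 90.7 | 91.1 |
| Moderate 0.3/0.3/0.5 | 2000 | 81.4 | 82.2 | 84.1 |
| | 2718 | 89.9 | 90.4 | 92.1 |
| Strong 0.4/0.4/0.8 | 2000 | 79.7 | 81.4 | 85.8 |
| | 2718 | 90.9 | 91.6 | 94.6 |

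The Monte Carlo standard error of one entry is √(0.8·0.2/3000) = 0.7 points at 2000 and √(0.9·0.1/3000) = 0.5 points at 2718. Compare within rows, where all three tests see the same simulated trials. The levels are noisier: the 81.4 in the first row lies 2 points above the closed-form 79.4.

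- Stratification factors alone: about 0 to 1.7 points.
- Baseline Barthel added: 0, 1.1, 2.7 and 6.1 points at 2000; 0.1, 0.6, 2.2 and 3.7 at 2718.

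Set A, 2718 patients, 2500 trials per cell, chi-square against logistic: 90.1 to 90.7 (weak, 0.2/0.2/0.3), 90.8 to 92.5 (moderate, 0.3/0.3/0.5), 90.8 to 93.8 (strong, 0.4/0.4/0.7).

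**Step 3: convert to patients.** Ratio = [(1.960 + z_adjusted)/(1.960 + z_chi-square)]², where z is the normal quantile of the power. From set A:

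- Weak: (1.960 + 1.323)² / (1.960 + 1.287)² = 10.78/10.54 = 1.02
- Moderate: (1.960 + 1.440)² / (1.960 + 1.329)² = 11.56/10.82 = 1.07
- Strong: (1.960 + 1.538)² / (1.960 + 1.329)² = 12.24/10.82 = 1.13

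The upper end follows the assumption. With 0.8 instead of 0.7 per SD of Barthel (set B, strong), the ratio is (1.960 + 1.607)² / (1.960 + 1.333)² = 12.72/10.84 = 1.17.

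**Step 4: type I error.** In set A, strong case, the chi-square rejects in 4.4% of null trials. The standard error is √(0.05·0.95/2500) = 0.44 points, so this is about 1.4 standard errors below 5%. In set B the chi-square ranges from 4.0% to 5.4% (standard error 0.4). Both extremes come from the strong case, at 2000 and 2718 patients respectively. The adjusted model ranges from 4.6% to 6.0%, and its highest value falls in the cell where the chi-square is also highest. No inflation of the chi-square is seen, and any conservatism is small.

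**The case against.** The strongest reply is that nothing here is wrong. The trial is sized for a Pearson chi-square and analysed with one, the test is valid, and the stated power is met. The adjusted odds ratio will be reported anyway. The gain depends on prognostic strengths that the protocol does not give, and the simulation treats Barthel as linear on the logit. That is doubtful when decline from baseline is part of the endpoint: a patient at 0 cannot decline, and, if the 10% is relative to baseline, a 5-point loss counts from 50 but not from 100. All of this stands. It makes the point one of efficiency and its size conditional. It does not remove the direction of the gain, and zero gain would require that the factors section 8.2 calls the main ones predict nothing.

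Four stronger readings are tempting and are not supported:

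- A reader might infer that ignoring the stratification makes the p-value invalid. Stratified allocation makes the arms more alike than the test assumes, so any error is towards caution.
- A reader might infer that the trial is underpowered. Step 1 of the working shows that it is not.
- A reader might blame the unused stratification factors. They account for at most about 1.7 points; most of the gain comes from Barthel, which is not a stratification factor.
- A reader might infer that the governing analysis is undefined if the two disagree near 0.05. Section 8.2 assigns the roles: the chi-square is primary and the regression estimates the effect. Changing the primary test would leave the same possibility of disagreement.

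**Conclusion.** The point holds as a nearly free improvement, not as an error. The chi-square is valid and delivers the planned power; what is given up is power beyond the plan. That is about 0 to 1.7 points from site and NRS alone, and about 0 to 6 points with baseline Barthel added. If the covariates are prognostic, the full gain is about 1 to 6 points at 2000 patients and 0.6 to 4 at 2718. At 2718 patients it is equivalent to roughly 2% to 13% more patients in set A, from weak to strong assumptions. The top of that range should not be quoted alone, because it moves with the Barthel coefficient assumed. The direction is secure; the size rests on assumed prognostic strengths, 8 sites, 3 NRS strata, blocks of 4 and a linear Barthel effect.

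**What to change.** In section 8.2 and in the SAP, which the protocol says will be finalised before database closure:

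- Name the treatment term of the logistic model with site, initial NRS category and baseline Barthel as the single primary test, at two-sided 5%.
- Keep the chi-square and the unadjusted odds ratio as supportive analyses.
- Report the standardised risk difference from the same model with its 95% confidence interval. The adjusted odds ratio is a conditional effect, whereas the trial is sized on marginal risks of 40% and 34%.
- Fix in advance how Barthel enters the model, how a missing baseline Barthel is handled, and how very small sites are pooled. The last is relevant because section 8.4 adds centres stepwise.

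The cost is a few sentences. No new data are needed, and the sample size of 1359 per group can stay, since it was computed for the less efficient test.

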#### Secondary endpoints will be defined as follows:

- (a) each single component of the primary endpoint at day 30
- (b) each single component of the primary endpoint and the combined endpoint at short term, ie, at day 10 or hospital discharge whatever comes first
- (c) each single component of the primary endpoint and the combined endpoint at long term term, ie, at day 180
- (d) short-term nutritional and functional outcomes from inclusion to day 10 or hospital discharge (whatever comes first) including nutritional intake, improvement in muscle strength measured with handgrip strength, lean body mass, changes in undernutrition markers (pre-albumin, retinol-binding protein, body weight, BMI)];

- (e) hospital outcomes measured at hospital discharge defined as total hospital LOS, discharge home vs. post-acute care facility, new decubital ulcer;
- (f) Improvement in quality of life measured on admission and at 30-day and 180-day using the EuroQol Group 5-Dimension Self-Report Questionnaire (Appendix 3) and selected items from the Functional Assessment Anorexia-Cancer Therapy [FAACT] questionnaire),

Safety endpoints including side effects from nutritional therapy will be assessed daily until hospital discharge. A causal relationship with the trial will be rated by two study team members as unrelated / unlikely / possible / probable / definitely / not assessable. The following side effects were defined:

- a) Adverse gastrointestinal effects (diarrhea, nausea, vomiting, abdominal pain)
- b) Complications due to tube feeding or center catheter for parenteral nutrition,
- c) Refeeding syndrome,
- d) Liver or gall bladder dysfunction
- e) Hyperglycemia (defined as glucose levels >12mmol/l or persistent levels >10mmol/l in patients without diabetes or well controlled diabetes)

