# 8. Statistics

# 8.1. Analysis population

The primary analysis population is the full analysis set, which, following intention-to treat (ITT) principles, includes all randomized patients. Every effort will be made to minimize the number of patients lost to follow-up.

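### The day-30 Barthel analyses have no rule for patients who die, so better survival can show up as worse function

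*Protocol*

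**What the plan says.** Protocol section 8.2 sets three analyses for Barthel's index. The unadjusted one reads "we will use a non-parametric Wilcoxon rank sum test to compare Barthel's index at day 30 between randomization arms". For adjustment, "we will also fit a multivariate linear model including Barthel's index at baseline, study center and initial NRS to estimate effect size". For the course over time, "we will assess the progression of Barthel's index over time (i.e. admission, day 8, day 30) using a linear mixed model approach". The same section compares primary and secondary endpoints in the overall ITT population, and section 8.1 says that this set "includes all randomized patients".

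Section 8.3 takes 10% mortality within 30 days as part of its planning estimate and hypothesises that early nutritional therapy lowers mortality. Section 4.2 and Appendix 1 define Barthel's index on a scale from 0 to 100. No section gives a rank or value for a patient who has died.

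For the remaining endpoints section 8.2 lists tests by type of outcome, among them "Wilcoxon rank sum test / linear models for continuous outcomes and log-rank test / cox regression for time-to-event data as appropriate". Section 4.2 lists "hospital outcomes measured at hospital discharge defined as total hospital LOS", without naming a method or a rule for in-hospital death. Section 8.2 also mentions a log transformation as an example of what may be done if needed, and leaves detailed methodology to an SAP that is not at hand.

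**The concern.** A patient who dies before day 30 has no Barthel score. A linear model on the day-30 score therefore drops that patient. Those who remain were selected after randomisation, by an outcome that the treatment is meant to change, so the arms are no longer comparable by design. The mixed model keeps a dead patient's earlier scores but handles the absent ones as ignorable missing data, in effect projecting function beyond death.

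The risk has a direction. If the intervention keeps frail patients alive, they enter its arm with low scores while their counterparts in the control arm disappear. A real survival benefit can then be read as functional harm.

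**Working it through.** **1. The plan's own figure.** Section 8.3 gives 1359 per group for 40% versus 34%, two-sided alpha 0.05, power 0.90. With pooled variance and no continuity correction:

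n = [1.960 × √(2 × 0.37 × 0.63) + 1.2816 × √(0.40 × 0.60 + 0.34 × 0.66)]² / 0.06² = (1.3382 + 0.8733)² / 0.0036 ≈ 1359.

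It reproduces. It concerns the primary composite; the protocol states no sample size or power for Barthel's index, so 1359 serves here only as an arm size.

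**2. Patients without a score.** At 10% mortality in both arms, 0.10 × 1359 ≈ 136 per arm have no day-30 Barthel score. Over the planned total of 2000 to 3000 that is 200 to 300 patients.

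**3. Direction and size in survivors.** Let control mortality be c and intervention mortality t, with t < c. Assume no effect on function in patients who survive under either arm (mean S), and let the rescued fraction c − t average g points lower. The control survivor mean is S. The intervention survivor mean is [(1 − c)S + (c − t)(S − g)] / (1 − t). Hence

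difference (intervention minus control) = −g × (c − t) / (1 − t).

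With c = 0.10 from section 8.3, and t and g assumed because the protocol gives neither:

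| g (points) | t = 0.085 | t = 0.07 |
|---|---|---|
| 25 | −0.41 | −0.81 |
| 45 | −0.74 | −1.45 |
| 65 | −1.07 | −2.10 |

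**4. A worked case.** Assume t = 0.08, rescued patients scoring 20 and all other survivors 80. The intervention survivor mean is (0.90 × 80 + 0.02 × 20) / 0.92 = 78.7 against 80.0, a difference of −1.3. With death scored 0, purely for illustration, the means are 72.4 and 72.0, a difference of +0.4. The sign changes.

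**5. Effect on the test.** A simulation used 400 runs per setting and 1000 or 1500 patients per arm. Scores were normal with SD 20, mean 85 for other survivors and 20, 40 or 60 for rescued patients, rounded to steps of 5 and capped at 0 and 100. A Wilcoxon test in survivors significantly favoured control in about 6% to 12% of runs at t = 0.085, and about 14% to 26% at t = 0.07, against a nominal 2.5%. With death ranked below 0 this fell to about 0.5% to 3%. The ranked test favoured the intervention in only about 3% to 12% of runs, so it removes the false signal of harm without adding much power.

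**6. Day 8.** The mixed model uses a Barthel score at day 8. Section 4.2 places the short-term assessment of the primary endpoint's components, functional decline among them, at day 10 or discharge, whichever comes first. Section 4.3 names day 8 for blood sampling. The times do not match.

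**7. Log transformation.** The scale includes 0, where the logarithm is undefined.

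**8. Length of stay.** If stay were analysed as a plain continuous outcome, each averted in-hospital death would lengthen the mean stay. Assume death on day 3 or 5, a stay of 10 to 20 days had the same patient lived, and t as in step 3. The difference is (c − t) × (stay if alive − day of death): smallest 0.015 × (10 − 5) ≈ 0.08 day, largest 0.03 × (20 − 3) ≈ 0.5 day, longer in the better-surviving arm. These figures treat all 30-day deaths as in-hospital and so lean high.

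**The case against.** The strongest reply is that section 8.2 is openly a summary and defers detail to the SAP, where the handling of deaths in a functional score normally sits. No sentence says that the dead are excluded. This stands in part: the SAP may contain a rule. But the protocol itself names the models, the population and the times, and a linear model on a score that about a tenth of patients cannot have does not cover all randomised patients unless death is given a value.

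Several stronger readings are tempting, and the documents do not support them:

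- A reader might infer that length of stay is assigned to Wilcoxon tests and linear models. It is not: the log-rank and Cox option is equally open.
- A reader might infer that the Wilcoxon test cannot accommodate deaths. It can, by ranking them worst; the text just does not say so.
- A reader might take the log transformation as a fixed choice. It is a conditional example.
- A reader might think a day-8 score impossible. Patients are assessed daily until discharge, so it could be collected; the fault is the mismatch with section 4.2.

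Two further points limit the impact. Adjustment for baseline Barthel would absorb part of the bias if rescued patients were already frail on admission. Mortality is also reported as an endpoint in its own right, and the continuous day-30 score is not listed separately among the secondary endpoints in section 4.2, so a reader would see survival beside function.

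**Conclusion.** The point holds for Barthel's index. With 10% expected mortality and a hypothesised mortality effect, analyses fixed without a rule for death let better survival of frail patients appear as worse function. The shift is about −0.4 to −2.1 points in the unadjusted survivor mean. That range rests on assumed intervention mortality (7% to 8.5%), an assumed gap of 25 to 65 points and no functional effect in patients who survive either way; it is not an estimate for the adjusted or mixed models. The protocol establishes the mechanism but not the size. If mortality does not differ between arms, the formula in step 3 gives no shift.

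Only secondary analyses are concerned. A reader might fear for the primary result, but death is itself an event in the primary composite, so that comparison and its sample size are untouched. For length of stay, the only supported statement is conditional: as a plain continuous outcome it would count in-hospital death as a short stay.

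**What to change.** In section 8.2, and in the SAP to match:

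- Compare day-30 Barthel in all randomised patients with death ranked worst, below a score of 0. Use the Wilcoxon test unadjusted, and an ordinal model (for example proportional odds) with the covariates already named: baseline Barthel, centre and initial NRS.
- Report the linear and mixed models as supportive, survivor-only analyses, labelled as such. For the label to be true, fit the mixed model in patients alive at day 30.
- Reconcile the day-8 Barthel with the day-10-or-discharge assessment in section 4.2.
- Drop log transformation as the example.
- State the method for length of stay. Time to discharge alive, with death as a competing event, fits within the time-to-event option already listed.

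The cost is a few sentences, with no change to sample size or to the primary analysis. The downside is that the ranked Barthel result mixes survival and function, which is why the survivor results should be shown beside it.
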